#### **10.4.3 Handling of missing values/censoring/discontinuations**

All efforts will be made to complete data except for cases of loss to follow-up, graft loss or death. Loss to follow-up, graft loss or death is defined as one whose last day of contact is prior to Month 24 and who did not experience graft loss or death. The missing data will be assumed to be missing at random except for above cases. The sensitivity analysis based on a complete case analysis and a missing data analysis will be conducted if imputed data exceeds 5 % of total data.

The modified last observation carried forward (LOCF) will be applied if eGFR has not been obtained at study visits. Only in cases where the observed measurement was obtained within 6 weeks of the expected study visit, modified LOCF will be employed to impute missing data. In other words, missing data will be replaced with data from out-of-window visit occur within 6 weeks of scheduled visit. None of data will be carried forward beyond 6 weeks, and will not be imputed by other methods. For the FAS analysis, this will be done regardless of whether a patient discontinued study medication or not. For patients experiencing graft loss, the last value before dialysis or re-transplantation will be used.

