## 7 Visit schedule and assessments

Table 7-1 lists all of the assessments and indicates with an “x” the visits when they are performed.

Patients should be encouraged to attend all visits on the designated day. However visit windows will be allowed of  $\pm$  1 day for Days 5 and 7,  $\pm$  3 days for Days 14, 21, and 28 visits,  $\pm$  1 week for Months 2 – 12 visits, and  $\pm$  2 weeks for Months 15 – 24 visits.

Patients who discontinue study drug before completing the study, and those who prematurely withdraw from the study for any reason, should be scheduled for a visit as soon as possible, at which time all of the assessments listed for the final visit will be performed.

Patients who discontinue study drug should also return for the assessments indicated in Table 7-1, including a blood sample for serum creatinine. If they refuse to return for these assessments or are unable to do so, every effort should be made to contact them or a knowledgeable informant by telephone when they refuse to return, and at 6, 12, and 24 months to determine the information on survival status, graft loss/re-transplant, rejection episodes, malignancies, opportunistic infections and immunosuppressive therapies. Since patients will be followed even after discontinuation of study medication, the Study Completion CRF page should only be completed at Month 24 or earlier if the patient can no longer be followed, e.g. death, lost to follow-up, or withdrawal of consent.

All patients will be contacted 30 days after the last dose of study medication regarding Serious Adverse Event information. Graft loss, death and malignancy are considered to be SAEs and should be entered on a SAE form and reported to the relevant regulatory authorities during the follow-up period (beyond 30 days after the last dose). Other Serious Adverse Events that are related to study medication as assessed by the investigator should also be entered on a SAE form and reported to the relevant regulatory authorities during the follow-up period.

Patients who prematurely discontinue study medication due to death, lost to follow up or patient withdrew consent will not have any post-study follow up evaluations.

At a minimum, patients will be contacted for safety evaluations during the 30 days following the last dose of study drug or last completed visit (whichever is later), including final contact at the 30-day point. Documentation of attempts to contact the patient should be recorded in the patient record.

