**Table 7-1 Evaluation schedule**

	SCR	OR	Day								Month											
	-21- 0	0	1	3	5	7	14	21	28	2	3	4	6	8	10	12	15	18	21	24		
Informed consent	X																					
Randomization	X																					
Background information	X																					
Inclusion/exclusion	X	X																				
Medical History	X	X																				
Transplant information		X																				
Viral serology	X												X		X		X	X			X	
Pregnancy test	X													X		X					X	
EKG		X																				
Vital signs		X	X	X	X	X	X	X	X	X	X	X	X	X	X	X	X	X	X	X	X	
Physical exam		X																	X			
Laboratory tests		X	X	X	X	X	X	X	X	X	X	X	X	X	X	X	X	X	X	X	X	
Renal Biopsy	X 												X 						X 			X
Study medication		X	X	X	X	X	X	X	X	X	X	X	X	X	X	X	X	X	X	X	X	
Campath dosage		X																				
Everolimus trough level					X	X	X	X	X	X	X	X	X	X	X	X	X	X	X	X	X	
Tacrolimus trough			X	X	X	X	X	X	X	X	X	X	X	X	X	X	X	X	X	X	X	
SF-36						X				X				X			X			X		X
Steroid	Per hospital protocol																					
Adverse events	As needed																					
Allograft rejection	As needed																					
Graft loss record	As needed																					
Dialysis log	As needed																					
Infection log	As needed																					
End of treatment	As needed																					
Comments	As needed																					
Follow-up record	Completed at 3, 6, 12, 18 and 24 months after the first dose of study medication for patients who prematurely discontinued study medication prior to Month 24.																					
Renal Biopsies	The study renal biopsy to be performed at 24 months. If clinically indicated biopsies were done prior to the scheduled biopsies at month 3, 12 and 24, repeat biopsy may not be performed.																					

OR: Day of transplant

Windows: Day 5, 7: ±1 day, Day 14, 21, 28: ±3 days, Month 2-12: ± 1 week, Month 15-24: ± 2 weeks

Biopsy windows: ± 4 weeks

1. Pre-transplant biopsy
2. 3-month and 1-year post-transplantation biopsies are performed as part of standard institutional protocol.

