#### **10.4.1 Variable**

The primary efficacy variable is the composite efficacy failure rate (treated BPAR, graft loss, death or loss to follow-up) at 6, 12 and 24 months post-transplant. The secondary variable is renal function assessed as eGFR during the first 24 months post-transplantation, determined by the MDRD formula. Other secondary variables include the incidences of CMV and BKV, new onset diabetes mellitus, chronic kidney disease with associated proteinuria, adverse events, serious adverse events and tacrolimus associated adverse events.

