#### **10.4.4 Supportive analyses**

Event rates will be compared between treatment groups using the Cochran-Mantel-Haenszel test, stratified by induction therapy.

A logistic regression analysis of the primary efficacy variable will be performed. The odds ratio for treatments, 95% confidence interval for the odds ratio, and p-values (if applicable) will be reported based on the fitted model.

A Kaplan-Meier survival analysis will be performed where all treated BPARs, graft losses, deaths or losses to follow-up that occur up to month 24 will be considered efficacy failures. The incidence of the composite efficacy failure (treated BPAR, graft loss, death or loss to follow-up) within 24 months will be compared between the two treatment groups using Kaplan-Meier probability estimates of efficacy failure and the associated 95% CI obtained

using the standard error derived by applying Greenwood's formula. The differences between the curves will be tested using the log-rank test.

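### Section 10.4.3 defines loss to follow-up in contradictory terms and with a single Month 24 cut, so the failure component is wrong at Months 6 and 12

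*Combined protocol and SAP*

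**What the plan says.** Section 10.4.1 makes the primary variable the "composite efficacy failure rate (treated BPAR, graft loss, death or loss to follow-up) at 6, 12 and 24 months post-transplant". Loss to follow-up is therefore a failure in its own right at three time points. Section 10.4.4 treats it the same way in the Kaplan-Meier analysis, where "losses to follow-up that occur up to month 24 will be considered efficacy failures". Section 10.5.1 also analyses death or loss to follow-up as a separate secondary variable.

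The only analytical definition is in Section 10.4.3. It takes loss to follow-up, graft loss and death together, and the patient it describes is "one whose last day of contact is prior to Month 24 and who did not experience graft loss or death". The next sentence exempts these cases from the missing-at-random assumption, so the same definition also decides which missing data get that assumption.

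Three other places bear on it:

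- **Visit windows.** Table 7-1 gives "Month 15-24: ± 2 weeks", and Section 7 agrees. Visits from Month 2 to Month 12 have a window of 1 week either side.
- **A second description.** Section 6.5.8 treats as lost those patients whose status is unknown because they stop attending and have not said that they wish to withdraw. It gives no date.
- **A closing safety contact.** Section 7 calls for a last contact 30 days after the final dose or the final completed visit, taking the later of the two.

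**The concern.** A definition that feeds a primary failure component must classify each patient in one way at each assessment time. This one does not. It names three outcomes and then requires that two of them did not happen. It also does not depend on the assessment month: Month 24 is the only reference point, although the composite is also read at Months 6 and 12.

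Patients known to be alive with a functioning graft at Month 6 or Month 12 could be counted as failures at those times because contact ended later. If such late losses differ between arms, the difference in failure rates moves with them. The trial is open label (Section 6.4), so a rule left to interpretation would be settled by people who know the assignments.

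**Working it through.** **Inputs.** Assessment months 6, 12 and 24 (Section 10.4.1). Windows of 1 week for Months 6 and 12 and 2 weeks for Month 24 (Section 7, Table 7-1). Closing contact at 30 days (Section 7). Arm size 16 (Section 10.6). Assumption: Month 24 is taken as day 730.

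**Arm size.** The plan's figure reproduces: 12 / (1 − 0.20) = 15. A block of 12 at 1:1:1 holds 4 per arm, so 15 rounds up to 16 per arm, and 3 × 16 = 48. Nothing here disputes that figure; 16 serves only as the denominator.

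**Step 1, internal logic.** The definition requires both no graft loss and no death. A patient with either event can never satisfy it, so it cannot define graft loss or death. Its only coherent content is a definition of loss to follow-up.

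**Step 2, the three assessment times.** Take an event-free patient whose last contact is at Month 20. The literal test (last contact before Month 24, no graft loss, no death) is met whichever month is being assessed. The alternative test asks whether last contact came before the lower window limit for that month.

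| Assessment | Literal rule | Cut at lower window limit |
|---|---|---|
| Month 6 | lost, failure | Month 20 is after Month 6 − 1 week: not lost |
| Month 12 | lost, failure | Month 20 is after Month 12 − 1 week: not lost |
| Month 24 | lost, failure | Month 20 is before Month 24 − 2 weeks: lost, failure |

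The literal rule is wrong at two of the three times. Applied to the final data, it gives the same set of lost patients at all three. If the Kaplan-Meier analysis dates a loss at last contact (an assumption, since Section 10.4.4 does not say), that curve shows this patient event-free at Months 6 and 12 while the rates at those months show a failure.

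**Step 3, the Month 24 window.** The earliest permitted Month 24 visit is day 730 − 14 = 716. A patient whose last recorded contact falls on days 716 to 729 is before Month 24 and literally lost. With the closing contact, last contact becomes at least day 716 + 30 = 746. That is after day 730, so the patient is not lost. Misclassification needs that contact to be missed, unrecorded or not counted.

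**Step 4, the two descriptions.** An event-free patient who withdraws consent at Month 10 and is not contacted again is lost under Section 10.4.3. Under Section 6.5.8 the same patient is not lost, because the intention to withdraw was stated.

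**Step 5, size.** One misclassified patient moves an arm's failure rate by 1/16 = 6.25 points. For 0, 1, 2 or 3 such patients (assumed counts) the shift is 0, 6.25, 12.5 or 18.75 points. Equal counts in two arms of 16 leave their absolute difference unchanged; each patient of imbalance moves it by 6.25 points.

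**The case against.** The intent is easy to guess: the sentence was meant to define loss to follow-up alone, and a sensible analyst would apply it by time point. Section 3.1 states the primary objective at 24 months only, and there the literal rule handles a patient last seen at Month 20 correctly. The protocol also uses Month 24 as a visit label, so a patient who attends an in-window Month 24 visit might naturally be taken as complete, and Section 6.5.8 would not call that patient lost. Much of this is fair, and it limits the seriousness of the point. It does not remove it: Section 10.4.1 puts Months 6 and 12 inside the primary variable, and the written rule gives the wrong answer there.

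A reader might infer something stronger: that patients who stopped study drug early and attend Month 24 within the early window are routinely scored as failures, more often in the arm with more discontinuation. The documents do not support this. Section 7 runs the closing contact from the last completed visit when that is later than the last dose, so it covers patients off drug too. Nor does the 20% drop-out rate in Section 10.6 give a count of misclassified patients: it inflates the sample size, and does not say how many patients stop drug but stay in follow-up, or when.

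Some uncertainty remains. Elsewhere in Section 7, and in the text on premature study discontinuation in Section 7.5, the 30-day contact is tied to last dose only. The synopsis plans no follow-up period. No section says whether a safety contact sets the last day of contact.

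**Conclusion.** The definition in Section 10.4.3 is wrong as written and should be corrected before anyone is classified. Two faults follow from the text alone: it excludes two of the outcomes it claims to define, and it applies one Month 24 cut to a component assessed at three times, which makes later losses count as failures at Months 6 and 12. It also conflicts with Section 6.5.8 on patients who state that they are withdrawing.

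The Month 24 window effect is a residual risk only, dependent on the 30-day contact being missed, unrecorded or not counted. No differential bias by drug discontinuation is shown.

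The number of patients affected cannot be obtained from the documents. The firm figure is 6.25 points per misclassified patient, assuming 16 analysed per arm.

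**What to change.** Replace the sentence in Section 10.4.3 with a definition of loss to follow-up alone, given separately for t = 6, 12 and 24 months: no graft loss or death by month t, and last contact before the lower limit of the visit window for month t (1 week before the scheduled date at Months 6 and 12, 2 weeks before at Month 24).

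Do not add a condition that the patient had no treated BPAR. Such a patient already counts once in the composite, and the condition would change the death or loss to follow-up variable in Section 10.5.1.

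Add three clarifications:

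- which contacts set the last day of contact (clinic visit, telephone contact with the patient or an informant, 30-day safety contact);
- whether withdrawal of consent counts as loss, with Section 6.5.8 worded to match;
- which cases the missing-at-random exemption covers, now that the definition refers to loss alone.

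The cost is a few sentences in Section 10.4.3 and an aligned sentence in Section 6.5.8. Sample size and visit schedule do not change.

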### **10.5.2 Safety**

Safety variables to be assessed include discontinuation from study, discontinuation from treatment, renal function, AE/infection, SAE, notable events, laboratory tests, and vital signs.

Comparison of calculated GFR using an analysis of covariance (ANCOVA) with baseline (Month 1) GFR as a covariate, and treatment and induction therapy as main effects, will be performed. Month 24 GFRs will be divided into three categories (<30, 30-60, >60) to classify chronic kidney disease. The proportion of patients in certain categories will be compared between treatment groups using the Cochran-Mantel-Haenszel test controlling for the Month 1 category.

Other safety variables include incidences of AEs, SAEs, new onset diabetes mellitus, CMV, BKV and proteinuria. These incidences will be compared between treatment groups using a Cochran-Mantel-Haenszel test, stratified by induction therapy. Urine protein/creatinine ratios will be compared between treatment groups using the Wilcoxon Rank-Sum test.

Additional assessments of safety will be based on the frequency of adverse events and on the number of laboratory values that fall outside of pre-determined notable ranges. Other safety data (e.g. vital signs and special tests) will be considered as appropriate. The data collected will be presented in listings, summary tables and graphs. All analyses will be performed on the SS.

Adverse events will be summarized by presenting, for each treatment group, the number and percentage of patients having any adverse event, having an adverse event in each body system and having each individual adverse event. The same type of summaries will be provided for serious adverse events and for events suspected to be related to the study medication. Any other information collected (e.g. severity or relatedness to study medication) will be listed as appropriate.

Laboratory data will be summarized by presenting shift tables using notable ranges (baseline to most extreme post-baseline value), by presenting summary statistics of raw data and change from baseline values (means, medians, standard deviations, ranges) and by the flagging of notable values in data listings.

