#### **10.6 Sample size calculation**

Since this is a pilot study, the sample size estimation method proposed by Julious was considered in order to minimize the sample size (14). Julious proposes to employ sample size of 12 per group for a pilot study (14). Assuming the drop out rate of 20% along with the ease of blocked randomization, we propose the sample size of 16 per arm, totaling 48 patients. The estimated effect size,  $\alpha$ , and  $\beta$  corresponding to this sample size are 0.9, 0.05 (two-sided), and 0.2 respectively (15). A block size of 12 along with an allocation ratio of 1:1:1 will be employed as a randomization scheme.

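### The missing-data check is triggered by imputed, not missing, values, so patients lost or withdrawn by Month 21 do not count towards it at Month 24

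*Combined protocol and SAP*

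**What the plan says.** All of the missing-data rules are in Section 10.4.3.

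- **Trigger and content.** The content is given as "The sensitivity analysis based on a complete case analysis and a missing data analysis". The condition for running it is that it "will be conducted if imputed data exceeds 5 % of total data". The section does not say what the total is, or what the second of the two analyses consists of.
- **Replacement of eGFR.** "Only in cases where the observed measurement was obtained within 6 weeks of the expected study visit, modified LOCF will be employed". The section then closes other routes: "None of data will be carried forward beyond 6 weeks, and will not be imputed by other methods".
- **Graft loss.** "For patients experiencing graft loss, the last value before dialysis or re-transplantation will be used". No time limit is given, and the sentence is not reconciled with the 6-week bar just before it.
- **Mechanism.** "The missing data will be assumed to be missing at random except for above cases". The excepted cases are loss to follow-up, graft loss and death.

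Section 10.5.2 gives the eGFR model: "Comparison of calculated GFR using an analysis of covariance (ANCOVA", with Month 1 GFR as covariate and treatment and induction as main effects. It names no visit for this model. Section 3.2 makes renal function at 12 and 24 months the key secondary objective.

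Section 7 ends follow-up after death, loss to follow-up or withdrawal of consent. Patients who only stop study drug are still followed, and Section 7.5 (premature study discontinuation and follow-up) schedules a serum creatinine for them at 6, 12 and 24 months.

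**The concern.** A sensitivity analysis for missing data should respond to how much is missing. Here it responds to how much has been filled in, while the same section forbids filling in most of what would be missing. A patient who disappears leaves a blank, and the blank does not count.

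eGFR carries the key secondary objective of an open-label trial whose discontinuation rules in Section 6.5.8 are partly specific to everolimus or tacrolimus, so unequal loss between arms is plausible. If patients with declining function leave follow-up more often in one arm, the comparison among those still measured favours that arm. The plan's one stated safeguard could stay silent in that situation.

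**Working it through.** **1. Planned size and dropout (Section 10.6).** 12 / (1 − 0.20) = 15 per arm. A block of 12 at 1:1:1 gives 4 per arm, so four blocks give 16 per arm, 48 in total. The plan's figure reproduces. (Sections 4 and 5 speak of 50 patients; 48 is used here.)

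**2. Reach of the 6-week rule.** With about 30.4 days per month:

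- Month 21 to Month 24: 3 × 30.4 / 7 ≈ 13 weeks, or about 11 if the Month 21 visit is at the late end of its 2-week window.
- Month 10 to Month 12: 2 × 30.4 / 7 ≈ 8.7 weeks, or about 7.7 with the 1-week window.

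All of these exceed 6 weeks. Without graft loss, the preceding scheduled visit can never supply the Month 12 or Month 24 value.

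**3. Month 24 as the denominator.** 0.20 × 48 = 9.6, about 10 patients. If none of them has a Month 24 eGFR:

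- missing: 10/48 = 20.8%, leaving 38 patients;
- imputed for these patients: 0/48 = 0%.

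The threshold is 0.05 × 48 = 2.4 values. Two imputed values (4.2%) do not reach it; three (6.25%) do. Three graft losses carried forward to Month 24 would start the check, while ten patients lost or withdrawn would not.

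**4. Other readings of the denominator.**

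| Reading | Values | 5% threshold |
|---|---|---|
| Months 2 to 24 (after the Month 1 baseline) | 11 × 48 = 528 | 26.4 |
| Chemistry time points in Section 7.5.8 | 17 × 48 = 816 | 40.8 |
| Post-transplant visits in Table 7-1 | 18 × 48 = 864 | 43.2 |

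Take the most generous reading of the 6-week rule, in which any last value within 6 weeks may be carried forward. On 864 values:

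- Ten dropouts last seen at Month 4 or later: 0 imputed.
- Ten last seen at Month 3: 10 × 9 = 90 missing (10.4%), at most 10 × 1 = 10 imputed (1.2%).
- Ten last seen at Day 5: 40 imputed (4.6%). At Day 3: 50 (5.8%). Only departure this early passes 5%.

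Graft-loss carry-forward passes 43.2 with 4 patients last measured at Day 28 (4 × 11 = 44), 5 at Month 3 (5 × 9 = 45) or 7 at Month 6 (7 × 7 = 49). On 528 values, 3 last measured at Month 3 suffice (3 × 9 = 27).

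**5. What the complete-case part would add.** An ANCOVA at a given visit already omits anyone without a value. A complete-case analysis removes, in addition, only the near-window and graft-loss substitutions. In the case in step 3, the ten absent patients are absent from both analyses.

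**6. Size of a possible bias (illustrative only).** The documents give no variance or dropout pattern. One simulation assumed a between-patient SD of 13, slope SD 0.5 per month, residual SD 6, a true Month 24 difference of 4.6 mL/min and dropout driven by the last observed eGFR. With 27% versus 7% missing, complete-case ANCOVA gave 6.6 and a likelihood model on all visits 4.75. With 15% versus 18% missing they gave 4.1 and 4.4. The simulation leaves out the graft-loss rule.

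**The case against.** A reader might infer that dropout can never trigger the check and that Month 24 eGFR rests on completers alone. The documents do not support that. The graft-loss sentence brings in the patients with the worst outcome, and their values count towards the 5%. Patients who stop study drug but remain in follow-up contribute observed Month 24 values. Section 7 also asks for an exit visit with the final-visit assessments; if it falls within 6 weeks of Month 24, its value can be used. So 20% missing is an upper planning case, not a forecast.

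It is also tempting to say that the ANCOVA fails under the plan's own missing-at-random assumption. The plan excludes loss to follow-up from that assumption. The accurate criticism is that, having set these patients apart, it names no eGFR method for them. Nor can the check be dismissed as only a complete-case analysis, since a second component is named, though undefined. The 864-value denominator is one reading among several.

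On scale, this is a secondary endpoint in a 48-patient pilot. Under the simulation's inputs the standard error of the Month 24 difference is about 5.5 mL/min, so the 2.0 overstatement (6.6 − 4.6) is about 0.36 of a standard error, and the two methods nearly agree when dropout is similar.

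These points narrow the concern. None makes the trigger respond to patients who are lost or who withdraw.

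**Conclusion.** The concern holds in limited form. The rule is defective as stated: it measures substitution, and the missingness that most needs a check produces no substitution at Month 24. That conclusion rests only on the visit spacing and the 6-week limit. The 20.8% missing against 0% imputed additionally assumes that every planned dropout lacks a Month 24 value and that no other values are substituted.

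If the 6-week bar is meant to override the graft-loss sentence, graft losses more than 6 weeks before the visit would not count either; the text does not settle this. The size of any bias in the eGFR comparison cannot be established from the documents. It would arise mainly if dropout differs between arms. This should be corrected before analysis, but it does not undermine the trial.

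**What to change.** In Section 10.4.3:

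1. Delete the 5% trigger and always run the sensitivity analysis. Failing that, base the trigger on the share of patients without eGFR at Month 12 or Month 24; at 5% of 48, three missing patients would start it. Define the second, unnamed analysis.
2. Make the eGFR analysis a likelihood-based repeated-measures model on all scheduled post-baseline values, with arm, visit, arm by visit and induction, reporting Month 12 and Month 24 contrasts. With 11 visits from Month 2 an unstructured covariance has 11 × 12 / 2 = 66 parameters, so name the fallback in advance, for example first-order autoregressive (allowing for unequal visit spacing) or compound symmetry.
3. Always add one delta-adjusted analysis for patients lost to follow-up or withdrawn, with the range of deltas fixed beforehand. It is needed because the likelihood model itself assumes missing at random for these patients.
4. State one rule for eGFR after graft loss and after death, and reconcile the graft-loss sentence with the 6-week bar. Otherwise the model implicitly extrapolates kidney function past those events.

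The cost is SAP wording and modest programming, and possibly a simpler covariance structure at n = 48. No new data are needed.

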### **3.2 Secondary objectives**

The key secondary objective is to compare renal function of the everolimus treatment arms to the MMF/MPA treatment arm at 12 and 24 months post-transplantation. Renal function will be measured by the calculated glomerular filtration rate (GFR), using the MDRD (Modification of Diet in Renal Disease) formula (20).

Other secondary objectives include:

- The incidence of treated BPAR at 12 months
- The incidence of graft loss at 12 months
- The incidence of death or loss to follow up at 12 months
- Incidence of adverse events (AEs)
- Incidence of serious adverse events (SAEs)
- Incidence of new onset diabetes mellitus defined as non-diabetic patients before transplantation, who are receiving glucose lowering treatment for more than 30 days

post-transplant, or with a random plasma glucose  $\geq 200$  mg/dL (11.1 mmol/L) with 2 fasting plasma glucose values  $\geq 126$  mg/dL (7 mmol/L).

- Incidence of CMV (viremia or viruria) and BKV (viremia or viruria)
- Incidence of proteinuria by more than 3 fold or proteinuria reaching 1.5gm/day
- The comparison of the health related quality of life for patients treated with everolimus plus low dose tacrolimus to CellCept plus standard dose tacrolimus

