#### **7.4.4 Graft Loss**

The allograft will be presumed to be lost on the day the patient starts dialysis and is not able to subsequently be removed from dialysis. If the patient undergoes a graft nephrectomy, then the day of nephrectomy is the day of graft loss. This will be reported on the premature discontinuation of study medication CRF, if medication is discontinued prematurely. The reason for graft loss will be recorded on the Graft Loss CRF. If graft loss occurs after the patient has discontinued study medication, the appropriate Follow-Up CRF should be completed. Graft loss is considered a Serious Adverse Event and should be reported on the Serious Adverse Event CRF and the SAE form must be reported to the relevant regulatory authorities within 24 hours.

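### Section 10.4.3 gives a lost graft its last eGFR before dialysis, with no time limit or floor and in conflict with the 6-week rule, so the eGFR comparison understates or omits graft failures

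*Combined protocol and SAP*

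**What the plan says.** Section 3.2 makes it the key secondary objective to "compare renal function of the everolimus treatment arms to the MMF/MPA treatment arm at 12 and 24 months post-transplantation", measured by MDRD eGFR.

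Section 10.4.3 fills a missing eGFR only from a measurement taken within 6 weeks of the scheduled visit, and adds: "None of data will be carried forward beyond 6 weeks, and will not be imputed by other methods". Two sentences later it gives a rule for lost grafts: "For patients experiencing graft loss, the last value before dialysis or re-transplantation will be used". That sentence has no time limit, no floor and no worst score. No other section scores eGFR after graft loss.

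Section 7.4.4 defines the event: "The allograft will be presumed to be lost on the day the patient starts dialysis", provided dialysis cannot later be stopped. A graft nephrectomy also counts.

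Section 10.5.2 analyses eGFR by ANCOVA with "baseline (Month 1) GFR as a covariate", and also by class: "Month 24 GFRs will be divided into three categories (<30, 30-60, >60) to classify chronic kidney disease". The class table is tested controlling for the Month 1 class. There is no class for dialysis or graft loss.

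The sensitivity analysis in 10.4.3 (complete-case and missing-data analyses) "will be conducted if imputed data exceeds 5 % of total data".

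**The concern.** After permanent return to dialysis, the state of the graft at Month 24 is not unknown. It has failed, and sections 6.5.8 and 7 provide for recording that even after study drug is stopped. The last-value rule replaces this known failure with a number from when the graft still worked. A patient at 45 in Month 1 whose graft is lost abruptly could stay at 45, stay in the 30-60 class, and appear not to have deteriorated.

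The trial enrols recipients of DCD kidneys and kidneys with KDPI of 70 or more, and compares regimens partly on how well they preserve function. If the arms differ in graft losses, or in the last values before loss, the eGFR contrast can point the wrong way.

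**Working it through.** **Inputs from the plan.** 16 patients per arm, 48 in total (sections 6.3 and 10.6). This figure reproduces: 12/(1 - 0.20) = 15, rounded up to 16 for blocking, and 3 x 16 = 48 = four blocks of 12. The plan gives no eGFR mean, SD or graft-loss rate, so everything below that needs one is an assumption.

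**Step 1: the two readings of 10.4.3.**
- *Graft-loss sentence as an exception.* The last pre-dialysis value stands in at every later visit, however old it is.
- *6-week limit governs.* A graft lost more than 6 weeks before the visit usually supplies no value, and the patient leaves the comparison.

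Neither reading represents the failed graft as failed.

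**Step 2: shift in an arm mean.** With *k* losses, last value *v*, and 0 as the reference score, the shift is *k* x *v* / 16 (unadjusted, all 16 patients contributing).

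| Losses | v = 15 | v = 25 | v = 35 | v = 45 |
|---|---|---|---|---|
| 1 | 0.9 | 1.6 | 2.2 | 2.8 |
| 2 | 1.9 | 3.1 | 4.4 | 5.6 |
| 3 | 2.8 | 4.7 | 6.6 | 8.4 |

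**Step 3: effect on the contrast.** Assume survivors average 55 in arm A and 50 in arm B, with two losses in A (last value 35) and none in B.
- Last-value rule: (14 x 55 + 2 x 35)/16 - 50 = 52.5 - 50 = +2.5
- Losses scored 0: (14 x 55)/16 - 50 = 48.1 - 50 = -1.9
- Complete cases: 55 - 50 = +5.0

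The arm that lost two grafts looks better under the plan's rule and better still if those patients are dropped.

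**Step 4: class table.** One patient is 1/16 = 6.25% of an arm. A loss with a last value of 30-60 puts that share in the middle class instead of the lowest.

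**Step 5: does the sensitivity analysis catch it?** Assume one imputed Month 24 value per loss and a denominator of 48. One loss is 1/48 = 2.1%, two are 4.2% and three are 6.3%, so one or two losses alone do not reach the 5% trigger. When it is reached, the complete-case analysis drops these same patients.

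**The case against.** The strongest reply is that graft loss is not hidden from the trial. It is a failure in the primary composite (10.4.1) and its Kaplan-Meier analysis (10.4.4), it is a secondary endpoint with its own tests (10.5.1), and it is a serious adverse event (7.4.4). This stands. A reader might infer that an arm could lose more kidneys unnoticed, and the documents do not support that. The defect is confined to eGFR.

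Other points, and what remains of them:

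- *Unlimited carry-forward is one reading.* Correct. An exception is the more natural reading, but the text does not say so. The alternative loses the patients instead.
- *A moderate last value is not certain.* Correct. Creatinine is scheduled often (7.5.8) and renal dysfunction calls for a biopsy (7.4.3), so a slowly failing graft may well have a last value below 30 and be classed correctly. Misclassification needs an abrupt loss with a last value of 30-60. The mean is still affected when the last value is low, but less.
- *A graft that never works need not drop out.* Correct. Creatinine is drawn on Day 1 and eGFR is calculated at each visit (7.5.8, 10.7), so a value may exist. The rule does not address this case, and the Month 1 covariate is a further obstacle.
- *Upward bias depends on the reference.* Correct. Against complete cases the last-value rule pulls the losing arm down (+2.5 against +5.0 in Step 3). Section 10.4.3 also excepts graft loss from the missing-at-random assumption, so the plan does treat it separately.
- *Zero is a convention, not an MDRD result.* Correct, and it has a cost. With 14 survivors at an assumed mean of 50 and SD of 15, two zeros give a mean of 43.75 and a variance of (13 x 225 + 14 x 6.25² + 2 x 43.75²)/15 = 486.7. The SD rises from 15 to about 22. Zeros at every visit would also zero the Month 1 covariate for early losses, so ANCOVA would adjust away part of the loss.

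**Conclusion.** The rule is wrong as written for an endpoint meant to describe graft function at Months 12 and 24. Depending on which sentence governs, failed grafts are scored as functioning or mostly omitted, and the triggered sensitivity analysis repairs neither.

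The figures in Steps 2 and 3 illustrate scale. They rest on assumed last values, survivor means and numbers of losses, on 16 contributing patients per arm despite the plan's 20% dropout, and on unadjusted means where the plan uses ANCOVA. Bias between arms arises only if losses or last values differ by arm.

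The documents do not support saying that every dialysis patient will be scored with moderate function, or that zero is the one correct main-analysis value.

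**What to change.** 1. **Reconcile 10.4.3.** State whether the graft-loss sentence is an exception to the 6-week limit, and cover grafts that never function.
2. **Class table in 10.5.2.** Place every patient with graft loss by Month 24, including grafts that never function, in the worst class: either <30 or a separate graft-loss class.
3. **Worst-rank comparison.** Prespecify a rank-based comparison of eGFR at Months 12 and 24 with graft loss ranked lowest, to be run regardless of the 5% trigger. It should not condition on Month 1 GFR for grafts lost before Month 1; leaving Month 1 GFR out of this comparison altogether is the simplest way. Report the last-value rule and a zero-value analysis alongside it.

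The cost is a few sentences in 10.4.3 and 10.5.2 and some extra analysis, with no new data, visits or patients. The zero-value analysis widens the SD, which is why the rank-based comparison is preferred.
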